Deep Brain Stimulation for Treatment-Resistant Depression

IRB# IRB00024883
Protocol Dated: 04/24/2018
NCT00367003

TITLE: Deep Brain Stimulation for Treatment-Resistant Depression

PRINCIPAL INVESTIGATOR: [name] [name] (Psychiatry)

CO-INVESTIGATORS: [name] (Psychiatry and Neurology)
[name], PhD (Neurosurgery)
[name] (Psychiatry)

DRAFT DATE: 4/24/2018

SCHEMA

Recruitment:	Telephone screening
Screening:	Eligibility assessment Informed consent and videotaping of consent process
Pre-operative Evaluation: (4-6 weeks pre-op)	Confirmatory psychiatric interview Neurosurgical evaluation 2-4 Behavioral Activation evaluations Neuropsychological testing #1 Emotional response testing #1 Activity Monitoring and GPS Route Logging #1 EEG testing #1 High-resolution anatomical MRI Diffusion tensor imaging Resting BOLD fMRI Weekly mood ratings
Surgery:	Pre-operative anatomical MRI Implantation of bilateral deep brain stimulators Intraoperative testing of DBS contacts with electrophysiological recordings LFP, EEG, HRV, SCR, EMG Implantation of pulse generator and lead extensions Post-operative anatomical MRI
Post-operative evaluation: (4 weeks post-op)	Stimulation OFF Weekly mood ratings for 4 weeks Emotional response testing #2 Activity Monitoring, GPS Route Logging #2 EEG #2 High resolution computed tomography (CT) scan
Open Stimulation:	Bilateral, open-label chronic stimulation (24 weeks) Emotional response testing #3-5 (1,3,6 months) Activity Monitoring, GPS Route Logging (1,3,6 mos) EEG #3-5 (1,3,6 months) Weekly mood ratings for four weeks Bi-weekly to monthly mood ratings for next 20 weeks Behavioral Activation therapy sessions (up to 30)
Ten Year Follow-Up:	Mood Ratings every month for 3 months, then Mood Ratings every 3 months for 9 months then Mood Ratings every 6 months EEG #6 Optional EEG at 6 months and at annual visits Gait assessment (once) Emotional response testing (once)

INTRODUCTION

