changes in visual perception. Although three patients had post-operative local wound infections, no other behavioral or medical adverse events were noted.

This pilot study supports the hypothesis that high-frequency DBS in Cg25 white matter can be used to treat depression, but further data is needed to confirm these findings. We propose a replication study at Emory University that will help further test the efficacy, safety and potential mechanisms of action of DBS for treatment-resistant depression (TRD).

OBJECTIVES

We propose to test whether high frequency DBS of the subgenual cingulate white matter (Cg25-DBS) is a safe and efficacious antidepressant treatment in forty TRD patients, and to investigate potential mechanisms of action of this intervention.

Importantly, this study will be used to assess the need for and assist in planning a larger, more definitive trial of Cg25-DBS for TRD. We will address the following specific aims.

Specific Aim 1. To assess the safety and tolerability of acute and chronic Cg25-DBS. Rates of complications (surgical complications, hemorrhage, stroke, infections, and seizures) will be assessed and compared to known rates for DBS surgery in other disorders.

Specific Aim 2. To assess the antidepressant efficacy of active Cg25-DBS in treatment-resistant depressed patients. We hypothesize that 24 Weeks of open Cg25-DBS will yield statistically significant antidepressant effects.

Specific Aim 3. To assess the possible mechanisms mediating Cg-25 DBS effects on depression. This will include behavioral and psychophysiological measures of emotional response and perception, motor activity and electrophysiological measurements with acute intra-operative testing of DBS.

Secondary Aim 1. To assess long-term effects of Cg25-DBS in patients with Major Depressive Disorder. Patients will be followed naturally over 10 years.

Secondary Aim 2. To assess for variables that predict antidepressant response, remission and relapse over time.

Secondary Aim 3. Changes in mood and behavior associated with DBS will have both immediate effects and slowly evolving, delayed effects, our experimental protocol will assess mood and behavior at several time points post-surgery. This will include behavioral and psychophysiological measures of emotional response and perception, motor activity and electrophysiological measurements.

PROTOCOL

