 - 3.3.5 Magnetic Resonance Imaging (MRI)(60 minutes). This pre-operative scan will help rule out intracranial abnormalities that might explain the patient's level of treatment resistance or preclude the patient from surgery. During this scan, we will also acquire diffusion tensor imaging (DTI) to assess white matter tract integrity and resting BOLD functional MRI data to assess regional connectivity.
 - 3.3.6 Neuropsychological testing (4 hours). A comprehensive neuropsychological battery will be administered by a trained psychometrist under the supervision of a board-certified neuropsychologist. This battery will take approximately 4 hours to

complete but can be done over more than one day if needed to prevent patient fatigue. The study will be performed prior to surgery and repeated at the end of 6 months of active stimulation

3.3.7 **Behavioral Activation:** In an effort to provide rehabilitation to our patients, behavioral activation therapy will be performed. There will be 2-4 sessions pre-op to establish a relationship with the patient. Therapy will begin post operatively when stimulation is started and will occur weekly for approximately 30 weeks.

3.4 **Mechanism of Action Studies.** To help assess mechanism of action (MOA) of DBS for TRD, several MOA experiments will be performed throughout the study beginning in the pre-operative evaluation period. All of the following will be repeated 1 month after surgery during acute DBS testing and again after 1,3, and 6 months of active DBS. :

3.4.1 **Emotional response testing with psychophysical measures.**

Eye-Tracking and Pupilometry: Eye-tracking will be used to measure the visual attention of the participant. The participant sits in front of a computer monitor and simply watches as pictures or sounds are presented. While they view the image or screen, a light beam is used to track the position and size of the pupil and cornea over time in order to estimate position of gaze.

3.4.1.1.1 *Emotional Pictures:* Emotional pictures will be selected from the International Affective Picture System, a standardized, widely available dataset, normed for content and emotional valence (IAPS; Lang, Bradley, and Cuthbert, 2008).

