6.0 Post-operative, Stimulation Off Phase (4 weeks)

6.1 Patients will be discharged with the DBS system off (patients will be told the system is off).

6.2 Patients will be evaluated weekly for four weeks to assess for behavioral changes following DBS surgery but prior to receiving active, chronic stimulation.

6.3 Clinical Assessments. During this phase, clinical assessments will include:

- 6.3.1 HDRS
- 6.3.2 HAS
- 6.3.3 MADRS
- 6.3.4 YMRS
- 6.3.5 BDI
- 6.3.6 BAI
- 6.3.7 IDS-SR
- 6.3.8 DAS
- 6.3.9 DOTS-R
- 6.3.10 BHS
- 6.3.11 Q-LES-Q (every 4 weeks)
- 6.3.12 HLQ (every 4 weeks)
- 6.3.13 TAS
- 6.3.14 C-SSS
- 6.3.15 SDS
- 6.3.16 PGI-S
- 6.3.17 PGI-I
- 6.3.18 CGI-S
- 6.3.19 CGI-I
- 6.3.20 Medication log

6.4 High Resolution x-ray CT scan: this study will be used to verify the final location of DBS electrode contacts needed for selection of the optimal contact for chronic stimulation.

6.5 Emotional response testing, actigraphy and GPS logging, EEG #2: Patients will return for repeat testing (same as 3.4.1-3).

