7.0 Open Stimulation Phase (4-30 weeks post-op)

7.1 Clinical Assessments. During this phase, patients will return every two to four weeks for clinical assessments to include:

- 7.1.1 HDRS
- 7.1.2 HAS
- 7.1.3 MADRS
- 7.1.4 YMRS
- 7.1.5 BDI

- 7.1.6 BAI
- 7.1.7 IDS-SR
- 7.1.8 DAS
- 7.1.9 DOTS-R
- 7.1.10 BHS
- 7.1.11 Q-LES-Q (every 4 weeks)
- 7.1.12 HLQ (every 4 weeks)
- 7.1.13 TAS
- 7.1.14 C-SSS
- 7.1.15 PGI-S
- 7.1.16 PGI-I
- 7.1.17 CGI-S
- 7.1.18 CGI-I
- 7.1.19 Medication log
- 7.2 Behavioral Activation Therapy: Patients will begin BA with the onset of stimulation. There will be a maximum of 30 sessions over the course of the first 6 months.
- 7.3 Emotional response testing #3-4: Patients will return for repeat testing at 1 month and 3 months of DBS. SCR and activity will be monitored continuously for the first month using the Q-Sensor mobile wrist sensor, 3-D accelerometer and Garmin mobile GPS devices. Weekly testing will be performed monthly for months 2-6.
- 7.4 EEG #3 and #4: EEG will be repeated at 1 month, 3 months of DBS.
- 7.5 End of Phase MOA Assessment. At the end of this 24 Week phase, patients will be evaluated as follows (see above for details):
 - 7.5.1 Neuropsychological testing #2
 - 7.5.2 Emotional response testing, actigraphy, GPS logging and EEG #5.
- 7.6 Programming Adjustments. Initial stimulation settings will be 130 Hz, 91 μ s pulse width, 4mA monopolar bilateral stimulation (one contact per electrode array per side). Every 4 weeks, after the clinical evaluation, a decision will be made whether to continue at these settings or make an adjustment. Adjustments will be made based on whether a patient is considered IMPROVED (>10% change in the 17-item HDRS score from the previous assessment and/or at least minimally approved on the CGI-I), UNCHANGED (\leq 10% change in the 17-item HDRS score from the previous assessment and/or unchanged on the CGI-I) or WORSE (>10% increased in the 17-item HDRS score from the previous assessment and at least minimally worse on the CGI-I) using the following algorithm:
 - 7.6.1 If IMPROVED, make no change and re-assess in 4 weeks.
 - 7.6.2 If UNCHANGED or WORSE, go through the following sequence of steps:
 - 7.6.2.1 Increase amplitude to 6 mA and reassess in 4 weeks.
 - 7.6.2.2 Increase amplitude to 8 mA and reassess in 4 weeks.
 - 7.6.2.3 Re-evaluate contact location and consider a contact switch; remain at 8 mA; re-assess in 4 weeks.

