9.0 Data Analyses and Statistical Consideration

9.1 **Definitions.** Standard criteria for antidepressant response, remission, relapse and recurrence will be applied⁴⁵.

- 9.1.1 **Response** will be defined as a decrease in the HDRS-17 score of 50% or greater from the average pre-surgical baseline.
- 9.1.2 **Non-response** will be defined as a <30% decrease in HDRS-17.
- 9.1.3 **Partial response** will be defined as a decrease in HDRS-17 >30% but less than 50%.
- 9.1.4 **Remission** will be defined as an HDRS-17 score <10.
- 9.1.5 **Depressive relapse** will be defined as meeting DSM-IV criteria for a MDE (i.e., meeting 5 of 9 DSM-IV criteria for 2 consecutive weeks with at least one symptom being depressed mood or anhedonia) in the absence of a 2 month period of remission. **Recurrence** will be defined as meeting DSM-IV criteria for a MDE following at least a 2 month period of remission.
- 9.1.6 **Study Success** will be defined by the number of patients meeting individual patient success criteria (HDRS-17 decrease of $\geq 50\%$ between baseline and 24 Weeks) after 6 months of active DBS. The study will be considered a success if 30% or more of enrolled patients meet the response criteria after 6 months of active stimulation. This threshold would exceed that seen for Vagus Nerve Stimulation, the only currently approved treatment for this degree of treatment refractory depression.

9.2 Statistical Analyses.

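### The 24-week result estimates Cg25-DBS given together with Behavioral Activation, so Specific Aim 2, the success rule and the Aim 2 analysis should not credit it to DBS alone

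*Combined protocol and SAP*

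**What the plan says.** **Timing of the therapy.** Section 3.3.7: "Therapy will begin post operatively when stimulation is started and will occur weekly for approximately 30 weeks". Section 7.2: "Patients will begin BA with the onset of stimulation". Before surgery the contact is introductory: "There will be 2-4 sessions pre-op to establish a relationship with the patient". The four-week post-operative phase (section 6.0) comes before stimulation, and so before therapy; it is unblinded, since "patients will be told the system is off".

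**Amount of the therapy.** Section 3.3.7 has weekly sessions over about 30 weeks. Section 7.2 has a ceiling: "There will be a maximum of 30 sessions over the course of the first 6 months". The schema also lists up to 30 sessions, under open stimulation.

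**What the result is said to show.** Specific Aim 2 is "To assess the antidepressant efficacy of active Cg25-DBS in treatment-resistant depressed patients". Section 9.1.6 declares success if at least 30% of enrolled patients respond after 6 months of stimulation, and supports that cut-off with "This threshold would exceed that seen for Vagus Nerve Stimulation". Section 9.2.4 compares HDRS-17 at baseline with HDRS-17 after 24 weeks and names only DBS as the treatment.

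**What is not said.** Section 9 contains no mention of Behavioral Activation: no caveat, no summary of sessions received and no sensitivity analysis.

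**The concern.** Two treatments start together in every patient treated as planned, and the response is measured against a baseline that has neither. A before-and-after comparison in one arm cannot tell them apart. The protocol accepts in principle that co-treatment matters: section 2.1.9 holds psychotropic doses stable through the 24 weeks. Yet it adds a structured psychotherapy at the moment stimulation begins and then words the conclusion as if DBS were the only new treatment.

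At stake is what the trial can be said to have shown. The Objectives say the study will help plan a larger trial, and 9.2.1 makes the size of the treatment effect the main focus. An effect size credited to DBS when it belongs to a two-part package would enter that planning under the wrong label.

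**Working it through.** **1. The plan's own figures.** Section 9.2.2 gives 11–19 patients to estimate a response rate of 4/6 = 0.67 to within 25 to 20 points. It states neither confidence level nor method. With a 95% Agresti–Coull interval, half-width = 1.96·√(p̃(1−p̃)/ñ), where ñ = n + 3.84 and p̃ = (np + 1.92)/ñ:

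- n = 11: ñ = 14.84, p̃ = 0.624, half-width 0.247, within 0.25.
- n = 19: ñ = 22.84, p̃ = 0.639, half-width 0.197, within 0.20.

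Both are the smallest n that qualify, so the stated range reproduces. At the planned 40 patients the half-width is about 0.14. The detectable effect of 0.68 at n = 19 also reproduces, with power 0.80 in a paired t-test at two-sided 0.05 (assumed, since neither level nor power is stated). These figures concern precision. A larger sample narrows the interval around the combined effect and does nothing to separate its parts.

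**2. Which periods carry which treatment, up to the endpoint.**

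| Period | DBS on | Behavioral Activation |
|---|---|---|
| Pre-operative | no | 2–4 introductory sessions |
| Post-operative, 4 weeks | no | not started |
| Open stimulation, 24 weeks | yes | yes, from the same starting point |

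No row has DBS without the therapy or a course of the therapy without DBS. The off phase gives some information on surgery and implantation, and none on the therapy. The change from baseline to week 24 is therefore DBS + Behavioral Activation + time and expectancy, and the design supplies no contrast that isolates the first term.

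**3. The two descriptions of the schedule.** Weekly sessions from the start of stimulation give about 24 by stimulation week 24. A weekly course of about 30 weeks would run some 30 − 24 = 6 weeks past the endpoint. Thirty sessions inside 24 weeks would be 30/24 = 1.25 per week. A ceiling of 30 is compatible with weekly sessions; what disagrees is the duration, about 30 weeks against 6 months.

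**4. When the therapy could decide the success rule.** Assume all 40 patients named in the Objectives form the denominator. The rule then needs 0.30 × 40 = 12 responders. With X binomial(40, p), where p is the true response rate under the combined treatment:

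| p | P(X ≥ 12) |
|---|---|
| 20% | 0.09 |
| 25% | 0.28 |
| 30% | 0.56 |
| 35% | 0.79 |
| 50% | 0.997 |
| 67% | above 0.999 |

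The documents give no response rate for Behavioral Activation, so any share assigned to it is an assumption. If, for illustration, DBS alone gave 25% and the therapy added 5 to 10 points, the chance of declaring success would go from 0.28 to 0.56 or 0.79. If DBS alone gave 50% or more, the same addition would leave the verdict where it was.

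**The case against.** The strongest reply is that the plan calls itself preliminary, a basis for comparative trials, and that every single-arm study is open to expectancy, regression to the mean and natural course. That is fair, and it is why the estimate should be described as the package plus time and expectancy. It does not cover the therapy, which is a specific added treatment that the analysis section leaves unmentioned.

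A second reply is that the therapy is described as rehabilitation and the patients are treatment-resistant, so its own effect may be small. That may be so. But 2.1.8.1 lists psychotherapy as one qualifying failure among several, so prior failure of Behavioral Activation is not required.

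Third, DBS and HDRS ratings continue for ten years, well past the end of therapy. That gives descriptive evidence on durability. It does not rescue the 24-week endpoint, and sections 8.4 and 8.5 allow medication and programming to change in that phase.

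Three stronger readings are tempting and not supported:

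- A reader might infer that a declared success would be owed to the therapy. Nothing in the documents sizes the therapy's effect, and the only 6-month response rate given, 4/6, lies far above the threshold.
- A reader might infer that the plan tests DBS against Vagus Nerve Stimulation. That device only supplies the reason for the 30% cut-off; section 9 plans no such comparison.
- A reader might infer that adjusting for cumulative sessions would separate the treatments. Sessions accrue with stimulation time, are counted after baseline and may depend on mood, so the term is nearly collinear with DBS exposure and could add bias.

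**Conclusion.** The point stands as one of attribution. The response rate and the HDRS-17 change can be computed and the 30% rule applied, but both describe DBS given with Behavioral Activation. Reading them as DBS alone, as Specific Aim 2, 9.1.6 and 9.2.4 do, is not supported by the design. This rests on the timing in 3.3.7 and 7.2 and needs no assumption about the size of the therapy's effect.

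The practical size is conditional. If the true rate is within several points of 30%, a modest contribution from the therapy could decide the success rule. At 50–67% it would not, though the effect size handed to the larger trial would still carry the wrong label.

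Two matters stay open. Section 10.1 reports 23 patients already implanted, and the documents do not say whether all of them received the therapy. Section 1.1.8 charges it to patients or payers, so the amount received may vary.

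**What to change.** 1. In Specific Aim 2, 9.1.6 and 9.2.4, state that the estimate and the success conclusion apply to Cg25-DBS given with Behavioral Activation and cannot be attributed to DBS alone. Add the same qualification to the Vagus Nerve Stimulation rationale in 9.1.6.
2. Record for each patient whether Behavioral Activation was received and the number of sessions to week 24, including the 23 already implanted where records exist. Report this descriptively beside the response rate. Do not use cumulative sessions as an adjusting covariate.
3. Reconcile the duration in 3.3.7 with the limit in 7.2, so that the amount of therapy up to the endpoint is unambiguous.

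The cost is a narrower claim and a simple session log. The assessment lists in 6.3, 7.1 and 8.3 have a medication log but none for therapy, so the log would be new. Care does not change.

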3.4.2.2 GPS logging. We also hypothesize that decreased depressive symptoms will be associated with an increase in patients' average level of daily life activities including amount of travel outside the home. This will be assessed by a wristband-style GPS route logger, which periodically logs the individual's GPS location, forming a connected route map of daily travels.

3.4.2.3 Security. Patients will be fully informed about the nature of the information that will be recorded, its purpose and use, and will be able to stop, pause, or start the GPS logging function whenever they wish, by pressing a button (patients will receive training on these functions). The GPS logging information will be securely transmitted to a cloud server that will store the route logging information associated with a random study identification number, not the individual's name or other identifying information. The information on the server is only retrievable using a login and password. The route logging information will be used to determine

the number, length, and complexity of travel outside the home.

3.4.2.4 Gait Assessment. We hypothesize that decreased depressive symptoms will be associated with increased gait speed and endurance. Patients will engage in a self-paced walk for six minutes while wearing sensors attached to the trunk and limbs (APDM Wearable Technology).

3.4.3. Electroencephalography. (EEG) (1 hour). This data will be tested in conjunction with the resting bold fMRI as a predictive biomarker of antidepressant response to chronic DBS and as an index of ongoing brain changes with short term and chronic DBS. This study will be performed at baseline, 1 month after surgery and during acute testing of optimal DBS contacts, after 1, 3 and 6 months of active DBS, and at one time point during the naturalistic follow up phase.

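### Protocol-required trips differ between the GPS windows and no rule removes them, so travel contrasts over time carry the visit calendar, in either direction depending on the comparator

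*Combined protocol and SAP*

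**What the plan says.** **Outcome and hypothesis.** Section 3.4.2.2 hypothesises that "decreased depressive symptoms will be associated with an increase in patients' average level of daily life activities including amount of travel outside the home". Section 3.4.2.3 says the route logs will give the "number, length, and complexity of travel outside the home". Neither section, nor section 9, says how trips to study visits or therapy sessions are handled.

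**GPS windows.** The schema lists "Activity Monitoring and GPS Route Logging #1" in the 4-6 week pre-operative evaluation, "Activity Monitoring, GPS Route Logging #2" in the four post-operative weeks with stimulation off, and further logging at 1, 3 and 6 months on stimulation. Section 7.3 adds continuous monitoring during the first month on stimulation and periodic monitoring in months 2-6. No GPS logging is listed for the ten-year phase.

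**Required attendance.**
- Pre-operative: ratings every 1 to 4 weeks, weekly in the last four (3.5), plus 2-4 BA sessions (3.3.7).
- Stimulation off: "Patients will be evaluated weekly for four weeks to assess for behavioral changes following DBS surgery" (6.2), with no BA.
- Stimulation on, ratings: the schema has four weekly ratings, then "Bi-weekly to monthly mood ratings for next 20 weeks". Section 7.1 gives visits every two to four weeks for the whole phase.
- Stimulation on, BA: "Therapy will begin post operatively when stimulation is started and will occur weekly for approximately 30 weeks" (3.3.7). Section 7.2 caps it at 30 sessions in the first 6 months.

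**Analysis.** Section 9.2.8 plans responder v nonresponder tests and longitudinal or pre-post models for EEG, emotional reactivity and psychophysiological variables. It does not name GPS travel.

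**The concern.** The hypothesis is about voluntary daily activity. A route to the clinic is travel outside the home, but it reflects the protocol and not the patient's mood. If every patient made the same number of required trips in every GPS window, this would only add a constant. The number is not constant, and BA starts at the same moment as stimulation.

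A contrast of travel between windows therefore mixes any treatment effect with a change in scheduled attendance. The plan names no comparator window for GPS, so both the size and the sign of this mixture depend on a choice that has not been made. In a repeated-measures model without a term for study phase, symptoms that fall after switch-on and required trips that rise at switch-on would be associated within patients through the calendar alone. Route length is affected too, and more so for patients who live far from the site.

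**Working it through.** The documents state no trip frequency, so there is no figure of theirs to reproduce. The check counts scheduled visits.

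**Assumptions not in the documents:** BA is in person, each BA session is a separate trip from the rating visit, and evaluation and testing trips are left out at first.

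**Step 1. Required trips per week = ratings + BA.**
- Pre-operative: (4 + 2)/6 = 1.0 to (4 + 4)/4 = 2.0. If all BA sessions fall in the last four weeks: (4 + 2)/4 = 1.5 to (4 + 4)/4 = 2.0.
- Stimulation off: 1.0 + 0 = 1.0.
- Month 1 on, schema: 1 + 1 = 2.0 to 1 + 30/24 = 2.25.
- Month 1 on, section 7.1: 0.25 + 1 = 1.25 to 0.5 + 30/24 = 1.75.
- Months 2-6 on: 0.25 + 1 = 1.25 to 0.5 + 30/24 = 1.75.

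If BA always shares the day of a weekly rating, month 1 is 1.0 to 1.25.

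**Step 2. Ratios of required trips.**
- Month 1 v off: 2.0-2.25 (schema), 1.25-1.75 (section 7.1), 1.0-1.25 (same day).
- Months 3 and 6 v off: 1.25-1.75.
- Month 1 (schema) v last four pre-operative weeks: 2.0/2.0 = 1.0 to 2.25/1.5 = 1.5.
- Months 3 and 6 v last four pre-operative weeks: 1.25/2.0 = 0.62 to 1.75/1.5 = 1.17. With the widest pre-operative range (1.0-2.0), the upper end becomes 1.75.

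**Step 3. Effect on total trips with no treatment effect.** Let the patient's own travel be constant at n trips a week (assumed). The apparent change is (n + required trips in the later window)/(n + required trips in the comparator) − 1.

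| n | Off to month 1, schema | Off to month 1, section 7.1 | Off to month 1, same day | Last four pre-operative weeks to months 3 and 6 |
|---|---|---|---|---|
| 2 | 33 to 42% | 8 to 25% | 0 to 8% | −19 to +7% |
| 3 | 25 to 31% | 6 to 19% | 0 to 6% | −15 to +6% |
| 7 | 12.5 to 16% | 3 to 9% | 0 to 3% | −8 to +3% |
| 14 | 7 to 8% | 2 to 5% | 0 to 2% | −5 to +2% |

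For n = 3: (3 + 1.25)/(3 + 1) − 1 = 6% and (3 + 2.25)/(3 + 1) − 1 = 31% bound the first two contrasts. For the last column, (3 + 1.25)/(3 + 2) − 1 = −15% and (3 + 1.75)/(3 + 1.5) − 1 = +6%. The off-to-months-3-and-6 range equals the section 7.1 column.

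**Step 4. Evaluation trips.** The pre-operative window also holds psychiatric, neurosurgical, imaging and neuropsychological visits, and the off phase holds a CT and repeat testing. With an assumed 3-7 extra trips pre-operatively, that window is (4 + 2 + 3)/6 = 1.5 to (4 + 4 + 7)/4 = 3.75 a week. The ratios against it become 0.53-1.5 in month 1 (schema) and 0.33-1.17 at months 3 and 6. With an assumed 1-3 extra trips in the off phase, that window is 1.25-1.75, and month 1 (schema) v off becomes 1.14-1.8. Testing trips in the on-stimulation windows are not added here and would push these ratios back up.

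**The case against.** A reader might infer that required trips double when stimulation starts, so that the hypothesised rise in travel is built into the design. The documents do not support that as a general statement. Doubling needs three things together: the off phase as comparator, the schema's weekly ratings, and BA as separate in-person trips. Section 7.1 gives a lower rating frequency, the documents do not say where BA takes place or whether it shares a day with ratings, and the doubling does not persist to months 3 and 6. Nor do they say that a DBS effect on travel is to be read from off to on. The pre-post wording in section 9 points as readily to the pre-operative window, against which the bias may vanish or reverse.

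Further points stand:
- The hypothesis is an association with symptom decrease. Responders and nonresponders share one schedule, so comparing them at one time point is not inflated by it. In a between-patient regression of change on change, a uniform shift goes into the intercept.
- That attendance is higher in patients who improve would be an assumption. The documents say only that the number of BA sessions has a maximum.
- The sentence on travel stands in a paragraph on data security and is not a formal endpoint definition. It is, however, the only place that says what is derived from the logs.
- The measure is exploratory, section 9.2.8 does not name it and calls its analyses underpowered, and study success rests on the HDRS-17.

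None of this supplies a rule for required trips, or makes the windows comparable in a pre-post or longitudinal contrast.

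**Conclusion.** The point holds in a direction-neutral form. The GPS outcome as written does not separate required from voluntary travel, and required trips differ between windows, so mean travel contrasts over time, and longitudinal models without a phase term, are biased by the visit calendar. From off to month 1 the bias is upward: about 6-31% of total trips at an assumed 3 own trips a week, across the schema and section 7.1, and 0-6% (0-8% at 2 own trips) if BA shares the day of a weekly rating. It shrinks as own travel grows. Against the pre-operative window at months 3 and 6 it may be null or downward, and could then hide a real increase. These figures rest on BA being in person, on the assumed own travel, and on leaving evaluation and testing trips out. No efficacy or safety decision depends on this measure, so priority is low.

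**What to change.** 1. In 3.4.2.2-3.4.2.3, define the GPS outcome as travel outside the home excluding routes to and from study visits and BA sessions, identified from visit dates and the site's location. Report total travel descriptively only.
2. In 9.2.8, name the GPS measures, their analysis and the comparator window.
3. Reconcile the schema with section 7.1 on how often ratings occur in the first four stimulation weeks.

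The cost is wording plus a location or date filter on data already collected. One small loss is that personal errands combined with a study or BA visit drop out of the measure.
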